Reach (Individual Level)	What percent of eligible participants: a) were excluded, b) took part and c) how representative were they?	Response rate and demographics
Effectiveness (Individual Level)	Effect of intervention on primary outcomes and QOL? Were pre-determined NHLBI guideline-based targets achieved?	Primary analysis (symptoms, quality of life; economic evaluation)
Adoption (Setting/Staff Level)	Characteristics of participating secondary schools, time and resource burden on school and community personnel.	School characteristics, demographics, staff surveys
Implementation (Setting Level)	To what extent were the various intervention components delivered as intended by school and community staff members?	Medication delivery log, session completion rate, contacts with nurses, surveys
Maintenance (Individual Level)	Long term effects at 12 months? Attrition rate? Were drop-outs representative; how did attrition impact conclusions?	Analysis of long-term outcomes (12 month assessment), attrition, demographics
Maintenance (Setting Level)	a)To what extent were intervention components continued post-study completion, b)how was the program modified	Survey and semi-structured interviews with school nurses, administrators, ALA leadership

12. Data Storage and Confidentiality

To maintain the integrity, security, and confidentiality of study data, the data will be maintained in a secure and encrypted web-based database and/or a password protected database on a secure university network drive. No subject data will be stored on the internal hard drives of any Strong Health computers. After data validation and analysis, subject information will be de-identified. All consent forms, paper surveys and additional correspondence will be locked in an office or filing cabinet and will only be accessible by the study staff.

Baseline, follow-up, and chart review data will be entered into a password-protected database. This database is stored on a secure university network drive that is only accessible by the research team whom must use their NetID and password to access the database. Data may also be collected and stored using RedCap, a secure, password protected database (using University NetID’s and passwords) hosted through the University of Rochester.

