This study is designed to have adequate power to test the primary hypothesis that teens receiving SB-ACT will have more symptom-free days at the 3, 5, and 7 -month evaluations compared to AE. Previous asthma interventions, including the SBAT trial, have demonstrated that improvements of 0.9 SFD/2 weeks are feasible and clinically meaningful.^{47,48} Based on our prior data, we estimate a pooled standard deviation (SD) of SFD to be 2.6 and within-subject correlation (ICC) of 0.3-0.4. We calculated power for the intervention effect on SFD while justifying repeated assessments for outcomes (5, 7, 12 months). A sample size of 123 subjects per group will obtain 94-96% power to detect a difference of 0.9 in SFD at a two-sided 5% significance level (assuming ICC: 0.3-0.4). We anticipate <15% attrition, as attrition was minimal (<5%) in the prior study, and therefore plan to enroll 430 teens. To test the short term intervention effect of DOT-only vs. AE, the sample size of 123 per group will obtain 80% power to detect a difference of 0.93/2 weeks at 3-month assessment with a two-sided 5% significance. We expect the DOT-only intervention won't sustain the effect at long term follow-up compared with AE. To test this, the proposed sample size will have 86% power at a one-sided 5% significance level, using a non-inferiority test with a margin of equivalence of 0.9 and a SD of 2.6. To compare the long-term effect of DOT-only vs. SB-ACT, we will have 80% power to detect an effect size of 0.4 at a two-sided 5% significance level.

To evaluate the intervention effect *within* each study arm, we anticipate in the SB-ACT group the rate of asthma control, asthma exacerbation and no absences will reach a guideline-based target of 80%. 123 subjects will have 80% power to claim a rate $\geq 80\%$ with a non-inferiority margin to be 10%, at a one-sided significance level of 5%.

There are 10,900 teens in 7th-10th grade in the city school district and >6,000 entering 7th graders in a 3 yr. period. Conservatively assuming an asthma prevalence of 10%,¹ >1,690 of these students have asthma, and approximately 1/2 have persistent asthma. In our prior study, we enrolled 74% of eligible subjects. We can conservatively enroll 126 subjects/year (60%); which is more than adequate for sample size requirements.

Primary Analysis:

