We will use graphs and descriptive statistics to summarize outcomes by intervention group at each time point. We will assess for differences between groups at baseline despite randomization (e.g., demographics, depressed mood, school/neighborhood factors) to enable the identification of covariates to be controlled in later analyses. If distributional

assumptions associated with a particular statistical procedure are violated, we will use appropriate transformations or non-parametric alternatives. Analysis will be performed under the intent-to-treat principle.⁴⁹ Hypothesis-driven comparisons will be made to control the family-wise type I error rate at 0.05 (2-sided) for primary hypotheses.

We expect minimal loss to follow-up.^{13,47,50} Inferences are valid if missing data follows the missing completely at random (MCAR) assumption.⁵¹ However, the occurrence of missing data may depend on the observed response, thus we will perform sensitivity analysis to examine the MCAR assumption. If it is severely violated, we will report treatment effects using weighted GEE to address MCAR. Biased estimates may also arise in the case of non-ignorable non-response (NINR). Although unanticipated, we will examine NINR using the joint modeling approach.⁵² For SEM, the maximum likelihood estimates (MLE) are valid under MAR, if the posited distribution models are satisfied. In the presence of missing data, estimates from LMM and SEM may be biased if parametric assumptions are not met, even with the use of robust variance estimates. If this arises, we will change the distribution models and/or use clustered bootstrap methods for inference.⁵³

REFERENCES:

3. *Expert Panel Report II: Guidelines for the Diagnosis and Management of Asthma-Update on Selected Topics 2002*. NIH publication no. 02-5075. Bethesda, MD: US Department of Health and Human Services; National Heart, Lung, and Blood Institutes; National Asthma Education and Prevention Program;2002.

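### The within-arm power sentence words its conclusion as a rate of at least 80%, but the test it describes can show only a rate above 70%

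*Combined protocol and SAP*

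**What the plan says.** The Sample Size and Power Justification in section 16 has a short paragraph on evaluating the intervention within each arm. Its premise is that "we anticipate in the SB-ACT group the rate of asthma control, asthma exacerbation and no absences will reach a guideline-based target of 80"%. It then states that "123 subjects will have 80% power to claim a rate" of at least 80%, "with a non-inferiority margin to be 10%, at a one-sided significance level of 5"%. The 70% boundary that follows from the target and the margin is not written down. Nor does the plan say that success means being no more than 10 points below the target.

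Two other places bear on this. The Effectiveness row of the RE-AIM table in section 11 asks: "Were pre-determined NHLBI guideline-based targets achieved"? It names no figure. The Primary Analysis text in section 16 says: "We will use graphs and descriptive statistics to summarize outcomes by intervention group at each time point".

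**The concern.** A non-inferiority test with a margin rejects the hypothesis that the rate is at or below the target minus the margin. Rejecting it supports a rate above that lower boundary and nothing stronger. The sentence gives the margin but names the target itself as the conclusion. Followed literally, it would let the trial state that the SB-ACT arm has a rate of at least 80% on evidence that the rate is above 70%. That could happen even when the observed rate is below 80%.

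What is at stake is the wording of a secondary, within-arm conclusion on asthma control, exacerbation and absences. The primary comparison on symptom-free days, the sample size and all between-arm results are untouched.

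**Working it through.** **Inputs, all from the power section.** n = 123; target and assumed true rate 80% ("will reach a guideline-based target of 80"%); margin "with a non-inferiority margin to be 10"%; level 5%, one-sided; stated power 80%; one arm against a fixed target.

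**Step 1. Reproduce the stated power.** Read the margin as absolute points, so the null rate is 0.80 − 0.10 = 0.70.

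- Normal approximation: z = (0.10 − 1.645·√(0.70·0.30/123)) / √(0.80·0.20/123) = (0.10 − 1.645·0.0413)/0.0361 = 0.888, which gives power 81.3%.
- Exact binomial: the smallest passing count is 95, because P(X ≥ 95 | 0.70) = 4.65% while P(X ≥ 94 | 0.70) = 7.04%. Power is P(X ≥ 95 | 0.80) = 81.2%.
- Number needed for 80% power by the same approximation: (1.645·√0.21 + 0.842·√0.16)²/0.10² ≈ 119, in line with 123.
- Using the null standard error throughout gives 78.1%; using the alternative standard error throughout gives 87.0%.

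The stated 80% is therefore reproduced with a null of 70%.

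**Step 2. Check the other reading of the margin.** If 10% were relative, the null would be 0.80 × 0.90 = 0.72.

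- Normal approximation: z = (0.08 − 1.645·√(0.72·0.28/123))/0.0361 = 0.372, power about 64%.
- Exact: the smallest passing count is 98 (size 3.3%), power 58.9%, or about 59%.

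Neither fits 80%. The absolute reading is an inference, but it is the one that agrees with the plan's own figure.

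**Step 3. What a pass shows.** The lowest passing result is 95/123 = 77.2%. Its exact one-sided 95% lower bound is 70.1%, and its two-sided 95% CI is 68.8% to 84.3%. The bound clears 70% and is well short of 80%. Results of 95, 96, 97 and 98 out of 123 (77.2% to 79.7%) pass with an observed rate under the target.

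**Step 4. How often the test passes when the target is missed.** P(X ≥ 95) at n = 123:

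| True rate | Chance of passing |
|---|---|
| 70% | 4.65% |
| 75% | 32% |
| 78% | 63% |
| 80% | 81.2% |

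In the 75% and 78% rows the target is not reached, so a claim of at least 80% would be false each time the test passed.

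**Step 5. For scale only.** The plan does not propose a test against 80%. One would pass from 107/123 = 87.0% (P(X ≥ 107 | 0.80) = 2.9%; P(X ≥ 106 | 0.80) = 5.02%) and would reach 80% power only at a true rate near 89%. So 123 subjects and a true rate of 80% cannot supply 80% power for the conclusion as worded.

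**The case against.** The best reply is that the sentence carries its own qualifier. Read to the end, it is compressed shorthand for non-inferiority to 80% within 10%, and any statistician can recover the 70% boundary from it. No number, test or sample size is wrong. That stands, and it is why the point is minor. It does not remove the point: disclosing a margin does not turn non-inferiority into attainment of the target, and the conclusion named is still not the one the test supports.

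A second reply is that the planned descriptive summaries by group will show the observed rates. This limits the harm, but it does not change the claim that the power sentence permits.

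Two stronger readings are tempting and should not be drawn.

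- A reader might infer that the RE-AIM question on guideline-based targets will be answered with this test. The documents do not say so. The assessment column of that row points to the primary analysis, covering symptoms, quality of life and the economic evaluation. It mentions neither 80% nor a within-arm test. The use is possible, because the power section calls its 80% guideline-based, but it is not stated.
- A reader might also take the share of trials landing between 95 and 106 of 123 at a true 80% (81.2% − 2.9%, about 78%) as an error rate. It is not one: at a true 80% the statement that the rate is at least 80% is true. In 47.1 points of that 78% the observed rate is itself above 80% (99 to 106 of 123); in the other 31.2 it is below (95 to 98). The relevant figures are the pass rates at true rates under 80% in Step 4.

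**Conclusion.** The point holds as a minor error of wording. The power is correct for a null of 70% and a true rate of 80%. A positive result shows a rate above 70%, non-inferior to the 80% target within 10 points, and not a rate of at least 80%. The gap matters in size: the test passes 32% of the time at a true 75% and 63% at a true 78%, and from an observed 77.2%.

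This rests on the margin being absolute, which the documents do not say but which the stated power supports. It also takes the exact binomial as the test, since no test statistic is named; the normal approximation gives nearly the same power. The finding does not extend to the sample size, the stated power or the primary analysis.

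**What to change.** Keep the 123 subjects, the test and the power. Replace the claim of a rate of at least 80% with wording such as: to show that the rate is non-inferior to the 80% target within 10 points (i.e. exceeds 70%). State that the margin is in absolute points.

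Define each endpoint in its favourable direction, for example no exacerbation. The present sentence lists asthma exacerbation among the rates meant to reach 80%, so a bare statement that the rate exceeds 70% would read literally as an exacerbation rate above 70%.

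Report each observed rate with its 95% CI beside 80%, and do not report the target as met on this test alone. If the test is meant to inform the RE-AIM targets question, say so there and apply the same limit.

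The cost is a change of wording, with no added participants or visits. The downside is that the permitted claim is less favourable.

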We will use portable spirometers and FeNO machines to measure the teen's pulmonary function and airway inflammation. Some teens may have difficulty with these procedures; we will only include data for teens able to perform the procedures accurately. We will use a portable scale and stadiometer to take objective measurements for height and weight.

Exposure to Secondhand Smoke will be assessed by both interview survey and cotinine measurements. A member of the research team will collect salivary fluid samples from each child using a small sterile swab. Collection will be made according to a standard protocol developed for use with children and adolescents. Salivary samples will be stored frozen and shipped via courier to Salimetrics, LLC in State College, PA for analysis. The Environmental Assessment will include a survey inquiring about environmental exposures and an observation checklist that a member of the study team will perform.

3. Randomization

Following the baseline assessment, each teen will be randomly assigned to one of 3 groups: 1) the SB-ACT program, which includes a trial of DOT plus a self-management MI counseling intervention; 2) DOT-only; or 3) an asthma education (AE) comparison group. *Randomization will be stratified by school and preventive medication at baseline.* Since enrollment will occur over a period of 1-5 months at the start of the school year, a permuted block design will be used to assure approximately equal allocation of teens in each group over time. The randomization scheme will be independently developed by a programmer in the Biostatistics Center. After baseline completion, the interviewer will call the study coordinator who will provide the subject's ID number and treatment assignment.

4. SB-ACT Intervention:

School Nurse Assisted Preventive Medication Use (Directly Observed Therapy)

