a) The primary outcome measure will be the number of symptom-free days (SFDs) at the 3, 5, and 7 mo. follow-ups. This outcome measure is consistent with the symptom monitoring suggested by the national guidelines,¹⁶ and we collected prospective data on SFDs in our prior studies, enabling a realistic calculation of sample size requirements. At each follow-up, parents and teens will report the number of days the teen experienced no symptoms of asthma (defined as 24 hrs with no coughing, wheezing, shortness of breath, and no need for rescue medicine) in the past 2 weeks. Symptom diaries will assist with recollection.

b) Secondary measures: Parents and teens will be asked to report the number of "steroid bursts" for asthma, as well as urgent (ED visits, hospitalizations, school exacerbations requiring treatment) and non-urgent (primary and specialist care) visits. With parent permission, we can access charts at each medical practice and will review medical records to verify visits. We also will measure the number of nights with asthma symptoms, days needing rescue medications, days with limited activity, and asthma control with the asthma control test (ACT).^{17,18}

Adherence: We will use Horne's adherence scale,¹⁹ and also will ask teens to report doses missed in the prior 2 weeks. To provide objective adherence data for teens in each group, we will monitor dose counters that are integrated into medication canisters. Almost all inhaled steroids now include counters, and in our prior study 99% of children used medication that included integrated counters. At baseline, 5-months, and 7-months, we will use home visits to document the number of doses on the teens' preventive medication inhaler (or count remaining pills for oral medications, i.e.; Singulair), and return 2 weeks later to re-measure the doses used. Based on the prescribed regimen, we will calculate adherence ($\#$ actuations / $\#$ prescribed) over the prior 2 wks. For teens in the SB-ACT and DOT-only groups, we will also collect school medication administration logs and will record the time to transition to independent medicine use.

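### Covariates are to be picked from observed baseline differences, and the primary symptom-free-day analysis is not committed to baseline symptoms or the two randomisation strata

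*Combined protocol and SAP*

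**What the plan says.** The covariate rule is in section 16, Primary Analysis: "We will assess for differences between groups at baseline despite randomization (e.g., demographics, depressed mood, school/neighborhood factors) to enable the identification of covariates". The full purpose of that check is "to enable the identification of covariates to be controlled in later analyses". The candidates are given only as examples: demographics, depressed mood, and school or neighbourhood factors. The section does not say what counts as a difference or which analyses are the later ones. It gives no model equation for SFD; the model families it mentions appear only in the missing-data paragraph.

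Section C.3 (Randomization) says: "Randomization will be stratified by school and preventive medication at baseline". No section carries either factor into the analysis, and none rules them out.

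The power section (section 16, Sample Size and Power Justification) gives the planning inputs: "we estimate a pooled standard deviation (SD) of SFD to be 2.6 and within-subject correlation (ICC) of 0.3-0.4". For the shorter-term comparison of DOT-only with AE it says "the sample size of 123 per group will obtain 80% power to detect a difference of 0.93/2 weeks at 3-month assessment". Neither statement mentions a baseline covariate.

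Baseline symptom items are collected (C.1, C.2 and the table in C.9). The two-week SFD count is described only for follow-up (C.8): "At each follow-up, parents and teens will report the number of days the teen experienced no symptoms of asthma".

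**The concern.** Under proper randomisation, any baseline difference between arms is due to chance. Its size says nothing about how strongly the variable predicts SFD, and it is prognostic strength that decides whether adjustment helps. A rule based on imbalance therefore selects on the wrong property, in two ways:

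- **Baseline symptoms.** If the screen were a p<0.05 test (an assumption, as the plan gives none), baseline SFD would enter the model in about 5% of trials, however well it predicts follow-up SFD.
- **The strata.** School and baseline medication are balanced by design, so a screen for imbalance tends to drop them. Where they are prognostic, an analysis that ignores them has standard errors that are too large and a conservative test.

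With no threshold and an open list, the adjusted set is also left to discretion after baseline data are seen. At stake is the precision of SB-ACT versus AE and of DOT-only versus AE at 3 months. Validity of a strictly applied rule is not at issue.

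**Working it through.** **Inputs from the power section.** SD 2.6; ICC r = 0.3 or 0.4; 123 per arm; difference 0.9 SFD (primary) or 0.93 SFD (DOT-only versus AE at 3 months); two-sided 5%.

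**Assumed input.** The correlation ρ between baseline SFD and each follow-up SFD is not in the documents. I take 0.1 up to the stated ICC. Selection of teens on current symptoms (section B) may narrow the baseline range and push ρ towards the low end.

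**Step 1: reproduce the plan's power.** For a mean of three visits, Var = 2.6² × (1 + 2r)/3, SE₀ = √(2·Var/123), and power = Φ(0.9/SE₀ − 1.96).

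- r = 0.3: SE₀ = 0.2421, power 96.1%.
- r = 0.4: SE₀ = 0.2568, power 93.9%.

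This matches the stated 94-96% with no covariate. With a common ICC any three visits give the same result, so the match does not show which visits were meant (the sentence reads "We calculated power for the intervention effect on SFD while justifying repeated assessments for outcomes (5, 7, 12 months").

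For a single visit, SE₀ = 2.6 × √(2/123) = 0.3315, and power at 0.93 is 80.1%, which matches the stated 80%.

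**Step 2: add baseline SFD.** The share of variance removed is R² = ρ²/[(1 + 2r)/3], and SE = SE₀ × √(1 − R²).

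| ICC | ρ | Variance removed | SE | Primary power |
|---|---|---|---|---|
| 0.3 | 0.1 | 1.9% | 0.2398 | 96.3% |
| 0.3 | 0.2 | 7.5% | 0.2329 | 97.2% |
| 0.3 | 0.3 | 16.9% | 0.2208 | 98.3% |
| 0.4 | 0.1 | 1.7% | 0.2547 | 94.2% |
| 0.4 | 0.2 | 6.7% | 0.2481 | 95.2% |
| 0.4 | 0.3 | 15.0% | 0.2368 | 96.7% |
| 0.4 | 0.4 | 26.7% | 0.2199 | 98.4% |

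At ρ equal to the ICC, leaving baseline SFD out is like analysing 123 teens per arm instead of 123/(1 − 0.169) ≈ 148 (ICC 0.3) or 123/(1 − 0.267) ≈ 168 (ICC 0.4).

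For DOT-only versus AE at 3 months the SE is multiplied by √(1 − ρ²). Power goes from 80.1% to 80.5, 81.7, 83.7 and 86.4% at ρ = 0.1, 0.2, 0.3 and 0.4.

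**Step 3: lower attrition.** The plan says "We anticipate <15% attrition, as attrition was minimal (<5%) in the prior study, and therefore plan to enroll 430 teens". At 5% attrition, 430/3 × 0.95 ≈ 136 per arm. Primary power goes from 97.4% to 97.7-99.0% (ICC 0.3) or from 95.8% to 96.1-99.0% (ICC 0.4). DOT-only versus AE goes from 83.9% to 84.2-89.6%.

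**Step 4: what an imbalance screen would achieve.** This was simulated with three arms of 123, an F-test on baseline SFD, and adjustment only if it was selected. There were 500,000 trials per three-visit cell, with ρ equal to the ICC, and 200,000 per single-visit cell. The p<0.05 and p<0.20 thresholds are assumptions.

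| Strategy | Primary power, ICC 0.3 | Primary power, ICC 0.4 | Type I error (ICC 0.3, 0.4) |
|---|---|---|---|
| Never adjusted | 96.0% | 93.8% | not tabulated |
| Screen p<0.05 (selected in 5%) | 96.3% | 94.3% | 4.7%, 4.5% |
| Screen p<0.20 (selected in 20%) | 96.8% | 95.5% | 4.4%, 4.0% |
| Always adjusted | 98.2% | 98.3% | not tabulated |

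For DOT-only versus AE, the p<0.05 screen gives 80.3% (ρ 0.3) or 80.5% (ρ 0.4), against 83.4% or 86.1% when always adjusted. The p<0.05 screen recovers little of the available gain.

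**Step 5: the strata.** The documents give no variance share for school or medication, so this gain cannot be computed. As illustration only, suppose the strata explain 1-5% of total SFD variance. The variance of the three-visit mean would then fall by about 2-9%, and a test ignoring them would run at about 4.8-4.0% instead of 5%.

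**The case against.** The strongest reply is that this is a missed gain in efficiency and not an error. An unadjusted randomised comparison is valid, and on the plan's own figures it has the stated power. **That stands**, and it limits the severity.

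Second, the rule speaks of later analyses and does not say that the primary test is among them; the p<0.05 screen is the reviewer's construct. This also stands in part. However, the rule sits under the Primary Analysis heading and is the only one the plan has. If the primary test is meant to be unadjusted, the plan does not say so, and the same precision is given up.

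Third, the larger gains need a correlation near the ICC. At ρ = 0.1 primary power moves by about 0.3 points. This stands. The larger gains for DOT-only versus AE also concern a comparison that the plan does not call primary.

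Fourth, the benefit from the strata is unquantified. With about 20 schools (section B) or 30 (Study Objectives) and two medication levels there are 40-60 cells of roughly 7-11 teens. Incomplete blocks may weaken the balance within cells, and with it the overstatement of the standard error. This stands as a caution on size. Naming school or neighbourhood factors as candidates does not answer the point, because it is no commitment to adjust for the school stratum.

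Last, a baseline covariate cannot be fully fixed until it is known which symptom item exists at baseline and whose report is used. That is true, and it is a reason to settle the matter in the SAP.

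**Conclusion.** The concern holds. The plan's only covariate rule selects on chance imbalance, has no threshold, and leaves baseline symptoms and both randomisation strata uncommitted.

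The consequence is conditional and moderate: less precision than the planned data allow, and an adjusted set chosen after baseline data are seen. On the primary comparison the forgone power is about 0.3 points at a correlation of 0.1, and about 2 points (ICC 0.3) or 4.5 points (ICC 0.4) at a correlation equal to the ICC. For DOT-only versus AE at 3 months it is 0.4 to about 6 points. These sizes rest on the assumed correlation range and on a two-week SFD count being available at baseline; with a different baseline item they may be smaller.

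The stated primary power is not in doubt, and a strictly applied p<0.05 screen does not raise type I error. The change is worth making because it costs almost nothing and removes the discretion at any correlation.

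**What to change.** Replace the imbalance rule with a fixed adjustment set, named before outcome data are seen, for the primary SFD model and for DOT-only versus AE at 3 months:

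1. The baseline symptom measure: the two-week SFD count if it is collected at baseline, otherwise the baseline symptom-day item. Check the baseline form and write in the one that applies, from the same reporter as the outcome.
2. Baseline preventive medication, coded as for randomisation (taken here as yes/no).
3. School, with the form of the term stated. A random intercept is one reasonable choice with about 20-30 schools.

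Keep baseline comparisons descriptive, and label models with further covariates as sensitivity analyses. The choice of contrast, visits, reporter and covariance structure is a separate matter.

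The cost is SAP wording and slight extra modelling. School and baseline medication are already needed for randomisation, and baseline symptom items are already collected. If the two-week count is not taken at baseline, the fallback may be on another scale (the eligibility item in section B is days per week over the past month), with a smaller gain.
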